11 ECONOMIC BURDEN TO PARTICIPANTS

11 LCONOMIC BORDEN TO PARTICIPANTS
11.1 Financial responsibility for research-related injuries. Answer this question only if the lead researcher is not a UW student, staff member, or faculty member whose primary paid appointment is at the UW.
Describe who will be financially responsible for research-related injuries experienced by subjects, and any limitations. Describe the process (if any) by which participants may obtain treatment/compensation.
11.2 Costs to subjects . Describe any research-related costs for which subjects and/or their health insurance may be responsible (examples might include: CT scan required for research eligibility screening; co-pays; surgical costs when a subject is randomized to a specific procedure; cost of a device; travel and parking expenses that will not be reimbursed).
No costs to subject
11.3 Reimbursement for costs. Describe any costs to subjects that will be reimbursed (such as travel expenses).
Subjects will be reimbursed for parking (up to \$9) or cost of public transportation on the day of the study
12 RESOURCES
12.1 Faculty Advisor. (For researchers who are students, fellows, or post-docs.) Provide the following information about your faculty advisor.
Advisor's name
 Your relationship with your advisor (for example: graduate advisor; course instructor) Your plans for communication/consultation with your advisor about progress, problems, and changes.
12.2 Study team communication . Describe how you will ensure that each study team member is adequately trained and informed about the research procedures and requirements (including any changes) as well as their research related duties and functions.
There is no study team.
We will hold regular study team meetings. During these meetings we will ensure study team members are informed and have the opportunity to perform all required study procedures as appropriate. We used this same method in our previous study to ensure ongoing adherence with all study protocols.

ZIPLINE APPLICATION: IRB Protocol

13 OTHER APPROVALS, PERMISSIONS, and REGULATORY ISSUES

13.1 Other regulatory approvals. Identify any other regulatory approvals that are required for this research, by checking applicable boxes

Do not attach the approvals unless requested by the IRB.

Approval	Research for which this is required	
Radiation Safety	Procedures involving the use of radioactive materials or an ionizing radiation producing machine radiation, if they are conducted for research rather than clinical purposes. Approvals need to be attached to the Supporting Documents page in Zipline .	
Institutional Biosafety	Procedures involving the transfer/administration of recombinant DNA, DNA/RNA derived from recombinant DNA, or synthetic DNA.	
RDRC	Procedures involving a radioactive drug or biological product that is not approved by the FDA for the research purpose and that is being used without an IND, for basic science research (not to determine safety and effectiveness, or for immediate therapeutic or diagnostic purposes).	
ESCRO	Procedures involving the use of some types of human embryonic stem cells.	
13.2 Approvals and permissions. Identify any other approvals or permissions that will be obtained. For example: from a school, external site/organization, funding agency, employee union, UW Medicine clinical unit. Do not attach the approvals and permissions unless requested by the IRB.		
Financial Conflict of Interest. Does any member of the team have ownership or other Significant Financial Interest (SFI) with this research as defined by UW policy GIM 10 ?		
proposed research? No → If no, conguidan Yes → If yes, FCOI won it is no	Research made a determination regarding this SFI as it pertains to your ontact the Office of Research [contact], [contact]) for ce on how to obtain the determination upload the Conflict Management Plan for every team member who has a with respect to the research, to the Supporting Documents page of Zipline . If t yet available, use the text box to describe whether the Significant ial Interest has been disclosed already to the UW Office of Research and a the FIDS Disclosure ID if available.	

#2003

## Cover

**Official Title of Study**: Prevention of Pressure Injuries During Aeromedical Evacuation or Prolonged Field Care

#NCT03924622

Date: 4 Jan 2019

Statistical Analysis Plan This study proposes to compare the effect of presence or absence of a Mepilex dressing) on variables (IL- $1\alpha$ /TP, TcPO2, interface pressure, skin temperature and moisture) potentially reflecting the modified effects of pressure, shear and microclimate associated with lying for an interval of (120 minutes) on either a standard NATO litter with mattress or a VSB. Primary analyses will contrast the Mepilex and non-Mepilex dressing groups, WITHIN the two support platform strata. That is, the two contrasts LITTER + Mattress (Mepilex vs. not) and VSB (Mepilex vs. not) will be the analysis foci. Analyses of the effect of support platform, and the interactions of platform with presence/absence of Mepilex pad will be considered secondary and exploratory. The statistical tests will be based on a group (Mepilex vs. non-Mepilex) by time (first sample – unloaded baseline, second sample post 120-minute loading) analysis. Analysis options depending on data structure include a repeated measures Group x Time ANOVA, an ANCOVA-based group analysis of the post-loading measurement controlled for the preloading measurement, a group analysis of the simple change score (post-loading – preloading), and a longitudinal analysis of the two-time points by group using Generalized Estimating Equations or a Linear Mixed Models. It is important to note that several of the studies using IL-1 $\alpha$  as a dependent variable have used non-parametric statistical tests. Similarly, error bar plots in published papers document a degree of heteroscedasticity, with the variability in a batch apparently having considerable dependence on its mean. This potential non-normality problem may be met with data transformation (e.g., square root or logarithmic transform) to an appropriate carrier or use of Generalized Linear Models with an appropriate non-linear monotonic link function, or the use of non-parametric statistics. As an example of application of the last method to the current data structures, the simple change score or residual change score from pre- to post- loading could be analyzed with the non-parametric Mann-Whitney U test. Power Analysis: The a priori justification of group sample size with respect to statistical power will be based on the potential change in the variable (IL- $1\alpha$ /Total ratio), which is measured in each participant immediately before and after lying for 120 minutes on the support platform. The analyses of other variables (e.g., TCPO2, interface pressure, skin temperature/moisture) will be treated as descriptive and secondary. When there is limited evidence in the literature that bear directly on the estimation of an effect size in planning a preliminary study, several authors and agencies have argued for setting the sample size per group N per group = 12.76-78 Assuming two tailed two independent group comparisons, with an adjusted significance threshold set to alpha = 0.025 to accommodate multiple testing at the alpha = 0.05 level for both the NATO litter and the "VSB" strata, and the size of each group N = 12, the minimum Cohen's d effect size per test necessary to achieve statistical power P = 0.80 is d = 1.336, which is considered a very large and ambitious effect size. However, there is related support in the literature that this level of effect is achievable using the proposed protocol. Hemmes55 (see Fig. 3, page 86, and Table A1, page 88) demonstrated that lying on either a rigid or soft-layered spineboard for 60 minutes raised mean sacral IL- $1\alpha$ /TP ratio by more than a factor of 10. de Wert24 (see Fig. 4A, page 510), using a 30- minute pressure and shear loading protocol on the forearm, showed that the presence of a Mepilex dressing resulted in IL-1 $\alpha$ /TP ratio levels that were on the order of 7 times smaller than the "no dressing" condition.

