Placement of Sensors: After completion of the height, weight and body fat measurements, the subject will lie down on the study surface and the temperature/oxygen sensors will be placed on the lower aspect of their back and one oxygen sensor placed on their chest (approximately 2 inches below the collar bone on the left chest). The transcutaneous oxygen (TcPO2) probes will heat up to 111°F, as recommended by the device manufacturer.

The subject will rest on their side for approximately 15 minutes while the measurements from the sensors to stabilize. These sensors allow for continuous measurement of skin tissue oxygenation and temperature.

Stabilization: Following acclimation, the subject will be assisted to a side lying position (unloaded) and the temperature and TcPO2 probes will be placed. Based on our previous research, it takes approximately 15 minutes for the sacral probe to stabilize ($TcPO_2 < \pm 2 \text{ mm Hg for 4 minutes}$).

Cytokine/Skin Moisture Measurements: After stabilization four small pieces of tape (Sebutape) will be placed on the lower back for 1 minute for the measurement of interleukin 1/Total protein. The Sebutape (size: 0.75 x 1.1 inches) will be placed in four quadrants (sacrum/buttocks). Sebutape has been used to measure IL- α in studies related to pressure and shear; including the evaluation of Mepilex under conditions of pressure and shear. Removal of the tape causes minimal stripping of the stratum corneum and discomfort to the subject. The Sebutape will be handled using blunt tweezers and gloved hands to avoid any cross contamination. Four patches will be applied (two on sacrum/two on buttocks) to intact, unblemished skin that is free of excessive hair, but which allows us to characterize potential injury on the buttocks and sacrum (areas of pressure injuries noted in Mok's study). After the one-minute sampling period the Sebutape will be removed using blunt tweezers and will be placed flat (avoid any crumpling or folding) into an individually labeled vial and immediately frozen on ice.

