Skin Moisture. We will also use a noninvasive probe to measure the amount of moisture in the skin on the lower back/sacrum. Two components of skin moisture will be measured: 1) Epidermal moisture, which reflects perspiration and 2) subepidermal moisture using a Delfin MoistureMeter D (Delfin Technologies, LTD, Grennwich, CT) dermal phase meter (http://www.delfintech.com/en/product_information/moisturemeterd/). Epidermal moisture (stratum corneum) will be measured at 0.5 mm below the skin surface and subepidermal moisture (i.e., below the epidermal stratum corneum layer) will be measured at a depth of 2.5 mm. The device consists of a control unit (signal producer) and a probe (open-ended coaxial transmission line), which is placed in contact with the skin The skin moisture will be measured at a standardized site, mid-sacrum, approximately 2 cm above the gluteal fold (avoiding the sites of the Sebutape). This location will be marked with ink pen to assure the same location for repeat measurement. For each depth, the probe will be placed on the skin surface and held for 5 seconds.

After these measurements are complete, subjects in the Mepilex dressing groups will have the dressing placed on their lower back/buttocks. All subjects will then complete an additional 5 minutes in the side-lying position, after which they will lie on their back on the designated surface. After positioning a sheet will be placed over the subject for comfort. A pillow may be placed under the head and heels at the subject's discretion.

The skin interface pressure will be measured continuously during the loaded period using the XSensor™ System (Crown Therapeutics, Belleville IL) with X3 Medical v6.0 software. This pad, which is similar to a sheet, will be positioned on the surface. *Peak skin-interface pressure*, which is the highest measured pressure for each body region and the *Peak Pressure Index* (PPI), which is the average of a 3 x 3 sensor area representing the highest pressure (including the peak pressure cell). The sacrum/buttocks will be divided into four quadrants based on the vertebral column and top of the gluteal cleft.⁵⁵ For the Mepilex groups, the pressure on the surface of the Mepilex will be recorded. Although this procedure does not directly measure skin interface pressure, which may be decreased by the Mepilex, it is not possible to place the pressure mat between the Mepilex and the skin.

Unique Procedures by Study Group

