For all groups the stretcher is placed on the bedframe of a standard hospital bed. The stretcher is secured to the bed frame. This elevation on the bedframe is for ease of access for the subjects. The bedframe is in the low position, such that the subjects will be approximately 2-3 feet off the floor.

Aeromedical Evacuation (AE) conditions

Group 1: Mepilex: Litter + AE mattress + 30° backrest elevation. Subjects will be positioned supine on the litter plus AE mattress. Mepilex will be placed on sacrum/buttocks region. Subjects will be asked to lie supine with

limited motion for 120 minutes. After completion of the 120-minute supine period, subject will be positioned side-lying. After 5 minutes side-lying, the Mepilex will be removed and the skin moisture and skin cytokine measurements will be obtained. After completion of the 15-minute side-lying phase, the skin sensors will be removed, and the study will be complete

Group 2: Without Mepilex: Litter + AE mattress + 30° backrest. Subjects will be positioned supine on the litter plus AE mattress. Subjects will be asked to lie supine with limited motion for 120 minutes. No Mepilex will be used. After completion of the 120-minute supine period, subject will be positioned side-lying. After 5 minutes side-lying the skin moisture and skin cytokine measurements will be obtained. After completion of the 15-minute side-lying phase, the skin sensors will be removed, and the study will be complete

AE Conditions with Vacuum Spine Board

Subjects in Groups 3 and 4 will be positioned on the vacuum spine board (VSB), which will be place on top of the litter + AE mattress. The litter will be elevated to 30 degrees (consistent with current practice). The vacuum will be applied according to manufacturer's recommendations. After creation of the vacuum, the VSB will be loosened around the head and feet to allow for movement for comfort. These steps do not interfere with the thoracolumbar stabilization or the interface pressure over the sacrum/buttocks. To simulate en-route care the vacuum will be maintained for 30 minutes (simulate movement to the aircraft). At 30 minutes, the

vacuum will be released with the straps in place (simulate current en route practice). At 90 minutes, the vacuum will be reapplied for 30 minutes to simulate descent and landing phase of flight (total time 120 minutes).

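### Must the SAP state which minutes of the continuous TcPO2 and skin temperature recordings form its two samples?

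*SAP*

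**What the plan says.** The SAP compares Mepilex with no Mepilex within each platform (litter with mattress; vacuum spine board). It lists IL-1α/TP, TcPO2, interface pressure, skin temperature and moisture as variables of interest. The time factor has two levels, "unloaded baseline, second sample post 120-minute loading". Several models are offered, to be chosen according to data structure; ANCOVA on the pre-loading value is one. The power section rests on IL-1α/TP only, and adds: "The analyses of other variables (e.g., TCPO2, interface pressure, skin temperature/moisture) will be treated as descriptive and secondary".

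Protocol section 5.1 gives the sequence. Probes are placed with the participant side-lying and unloaded, and "it takes approximately 15 minutes for the sacral probe to stabilize". Of the probes it says: "These sensors allow for continuous measurement of skin tissue oxygenation and temperature". Baseline tape and moisture measures follow stabilisation. Only then "subjects in the Mepilex dressing groups will have the dressing placed on their lower back/buttocks". Next, "All subjects will then complete an additional 5 minutes in the side-lying position", and then the 120 supine minutes begin. Afterwards, in Groups 1 and 3, "After 5 minutes side-lying, the Mepilex will be removed and the skin moisture and skin cytokine measurements will be obtained". The recording ends later: "After completion of the 15-minute side-lying phase, the skin sensors will be removed".

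**The concern.** Load and dressing do not change at the same moments. In a Mepilex participant the unloaded time before lying down has an undressed part and a dressed part, and so does the unloaded time afterwards. A sample definition that mentions load only does not say which part is meant.

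Two choices could mislead. A baseline taken in the last 5 unloaded minutes already contains any effect of the dressing, in the Mepilex arms only, so adjusting for it would remove part of what is being studied. A second reading taken while side-lying describes recovery, and after the first 5 minutes it does so with the dressing gone. Aim 1 (Protocol section 1.5) asks about oxygenation and temperature with and without Mepilex under simulated evacuation. A null TcPO2 or temperature result might then reflect the minutes chosen. Read strictly, a sample taken after loading excludes every loaded minute.

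**Working it through.** **The plan's own figure.** Inputs from the SAP: 12 per group, two-sided alpha 0.025, power 0.80. Exact two-sample t-test with 12 + 12 − 2 = 22 degrees of freedom and noncentrality d × √(12/2). Solving for power 0.80 gives d = 1.3360; at d = 1.336 the power is 0.79997. The figure reproduces. It concerns IL-1α/TP only.

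**Timeline in the Mepilex arms (Protocol section 5.1).**

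| Period | Length | Load | Dressing |
|---|---|---|---|
| Probe stabilisation | about 15 min | off | off |
| Baseline tape and moisture | not timed as a block | off | off |
| Wait after placement | 5 min | off | on |
| Supine | 120 min | on | on |
| Side-lying, first part | 5 min | off | on |
| Side-lying, second part | 15 − 5 = 10 min | off | off |

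**Possible readings.** Two baselines (undressed, dressed) and three second readings (end of minute 120, first part of side-lying, second part) give 2 × 3 = 6 pairs. Two of the six have a second reading with the dressing under load. If the second sample must come after the load is removed, 2 × 2 = 4 pairs remain and none does. This counts possibilities; it does not measure how likely a poor choice is.

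**What the documents already narrow down.**

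1. *Baseline.* Section 5.1 defines stability for the sacral probe (within 2 mm Hg for 4 minutes). The baseline tape and moisture measures come after that point and before any dressing. Taking TcPO2 and temperature at the same stage is the natural reading, and it leaves 3 of the 6 pairs.
2. *Second reading.* The paired-sample wording fits the tapes, which are applied to the skin of the sacrum and buttocks with the participant on the side. Continuous sensors have no such limit. Section 10.8 likewise lists cytokines and moisture as post-measures, separately from the final oxygen and temperature readings. With Aim 1 in view, the end of minute 120 is the obvious choice, when load is on and the dressing has been on for 5 + 120 = 125 minutes.
3. *Comparability.* On the vacuum spine board the vacuum is on for minutes 0–30 and 90–120 in both Groups 3 and 4. An end-of-load reading therefore compares like with like within that platform.
4. *Interface pressure.* It is recorded only under load, so it has no unloaded baseline. The SAP's model list depends on data structure, and section 5.1 already defines peak pressure and Peak Pressure Index. A direct between-arm comparison is what remains.

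**How much a poor choice could cost.** The documents give no response times and do not say whether the dressing covers the sensors. Assume exponential response with time constant τ = 5, 10 or 20 minutes, sensors under the dressing, and a change score. Results are fractions of the true arm difference at minute 120.

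- Effect only under load, read 5 minutes into side-lying: exp(−5/τ) = 0.37, 0.61, 0.78. Read at 15 minutes: exp(−15/τ) = 0.05, 0.22, 0.47.
- Effect from the dressing alone, undressed baseline, read at 5 minutes of side-lying with the dressing still on: about 1.00, so nothing is lost. Read at 15 minutes, 10 minutes after removal: exp(−10/τ) = 0.14, 0.37, 0.61.
- Effect from the dressing alone, dressed baseline with minute 120: 0.37, 0.61, 0.78. Dressed baseline with the end of side-lying: −0.50, −0.03, 0.38.
- Undressed baseline with minute 120: 1.00 in both cases.

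Losses appear only when an analyst leaves the choices in steps 1 and 2. Cancellation or reversal needs the less natural baseline, the latest reading and τ of 10 minutes or less, all together.

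**The case for a change.** The best case for a change is that these are Aim 1 outcomes and even a descriptive between-arm summary needs a defined window. The SAP already leaves the model open, and an open window adds a second choice that could be made after seeing the data. The most literal reading of the second sample is also the least useful one for Aim 1. Stating the window would cost a sentence and no new data.

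The textual part of this stands: no minute is written down for completers, and the only final reading tied to an event is the one at withdrawal in section 10.8.

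The rest carries less weight. A side-lying reading answers a different question, about recovery; it is taken on the same clock in every arm of a randomised comparison and is not an error. The 15-minute settling time in section 5.1 refers to a freshly placed probe and does not show how fast a settled probe responds to unloading. The TcPO2 electrode is itself heated to 44°C, so an argument from insulation does not carry over simply from skin temperature. Every attenuation figure rests on assumed response times and sensor position.

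**Conclusion.** The gap is real but small, and the plan can stand. The SAP leaves the reading window for TcPO2 and skin temperature unwritten. The protocol's sequence supplies a sound baseline (stabilised, undressed) and Aim 1 supplies a sound second reading (end of the 120 loaded minutes), both from recordings already planned. Side-lying values can be shown as recovery. ANCOVA is already among the SAP's options.

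Nothing stated in the plan changes: d = 1.336 is reproduced, IL-1α/TP has fixed sampling times, and the affected variables are descriptive and secondary. This conclusion assumes that analysts use the same clock window in every arm and report which one they used. The size of any distortion from another choice cannot be determined from the documents.

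### The SAP leaves the primary IL-1α/TP test and scale to a menu of options that are not interchangeable; one baseline-adjusted test should be named for each contrast

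*SAP*

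**What the plan says.** The SAP is one section. It fixes a good deal: two primary contrasts, each comparing Mepilex with no Mepilex within one support platform; two time points, unloaded baseline and after 120 minutes of loading; IL-1α/TP as the variable that sets the sample size, with all others descriptive and secondary; 12 per group; and two-tailed testing "with an adjusted significance threshold set to alpha = 0.025 to accommodate multiple testing".

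It does not fix the test. "Analysis options depending on data structure include a repeated measures Group x Time ANOVA", and the list goes on to ANCOVA of the post-loading value on the pre-loading value, a simple change score, and a longitudinal analysis "by group using Generalized Estimating Equations or a Linear Mixed Models".

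It does not fix the scale either. Citing published IL-1α data "with the variability in a batch apparently having considerable dependence on its mean", it says: "This potential non-normality problem may be met with data transformation" (square root and log are the examples), or "use of Generalized Linear Models with an appropriate non-linear monotonic link function", or non-parametric statistics. As an example of the last, simple or residual change "could be analyzed with the non-parametric Mann-Whitney U test".

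The protocol has no analysis section that narrows this.

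**The concern.** Splitting alpha across two contrasts controls error only if each contrast has one test, or one rule that leads to one test. The SAP names triggers (data structure, non-normality, spread that rises with the mean) but gives no threshold, no order of preference and no statement that the choice is made without group labels.

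Two things are at stake. The first is the stated 0.025. It would be exceeded if the choice followed the results, and at least one listed method can exceed it at 12 per group even when named in advance. The second is power. The options do not have equal power at the planning effect, so the stated 80% belongs to some of them and not to others, and with 12 per group the choice can decide whether a contrast is declared significant.

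**Working it through.** **Inputs from the SAP.** n = 12 per group, two-sided alpha 0.025 per contrast, power 0.80, d = 1.336, two time points.

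**Assumed, because the documents give none.** Lognormal or gamma data, CV 0.75-1.5, pre/post correlation 0.2-0.5, 10-fold rise under loading, equal pre and post SDs on the log scale. For tests on log-transformed lognormal data only the correlation (taken on the log scale) matters.

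**1. The plan's own figure.** A two-sample t-test with 22 degrees of freedom (critical value 2.405) and noncentrality d·√(12/2) reaches 80% power at d = 1.336. The figure reproduces.

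**2. Which options are distinct.** With two time points and complete data, the Group x Time ANOVA interaction is the change-score t-test. A mixed model gives the same estimate, but the same test only with matching degrees of freedom; with a z reference its error is 2·P(t22 > 2.2414) = 3.5%. ANCOVA, rank tests, GEE and each change of scale are separate choices.

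**3. Power at d = 1.336 in SDs of the log value.**

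- Log change: the effect in SDs of change is 1.336/√(2(1 − r)). At r = 0.2 this is 1.336/√1.6 = 1.056, power 58%. At r = 0.5 it is 1.336/√1 = 1.336, power 80%.
- Log ANCOVA: the residual SD is √(1 − r²), with 21 degrees of freedom. At r = 0.2 the effect is 1.336/0.980 = 1.364; at r = 0.5 it is 1.336/0.866 = 1.543. Ignoring chance baseline imbalance, power is 81% and 90%. Averaged over that imbalance it is 79% and 89%, and simulation agrees.
- Disagreement on significance between the two, simulated: 27% of trials at r = 0.2 and 13% at r = 0.5. At r = 0.2, log ANCOVA alone is significant in 24% of trials and log change alone in 3%.
- Log ANCOVA and Mann-Whitney on change disagree in 8-12% of trials.

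**4. Power if d is in SDs of change (normal data).** The change score has 80% by construction. ANCOVA has 95% and 89% (r = 0.2 and 0.5) with equal pre and post SDs, and 78% and 86% if the post SD is ten times the pre SD. The options still differ.

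**5. Error of GEE fixed in advance.** The usual robust variance of the Group x Time term divides each group's sum of squares by n instead of n − 1. With equal groups, z = t·√(12/11), so |z| > 2.2414 means |t| > 2.2414·√(11/12) = 2.146. On normal data the error is 2·P(t22 > 2.146) = 4.3%; simulation on log change gives 4.2-4.5%. Over two independent contrasts this is 1 − (1 − 0.0432)² = 8.4%, against 1 − 0.975² = 4.9% as planned.

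**6. Error of other routes (nominal 2.5% per contrast).**

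| Route | Error |
|---|---|
| One fixed t-test, ANCOVA or Mann-Whitney | 1.2-2.7% |
| Group-blind skewness rule | 2.1-2.7% |
| Normality-triggered switch | 2.5-2.9% |
| Better of log ANCOVA and Mann-Whitney on change, by result | 3.1-3.8% |
| Better of log change and log ANCOVA, by result | 3.3-4.2% |

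**The case against.** The best defence is that the flexibility is reasonable and mostly harmless. The SAP describes its planning as that of a preliminary study, the distribution of IL-1α/TP is not known in advance, and the text is not empty: it commits to a group-by-time frame and gives reasons for departing from it. A switch made on distribution alone roughly holds the level (step 6), and choosing between two close tests by result costs only one to two percentage points. Power "will be based on the potential change in the variable", so change is the natural reading of d, and on that reading the change score has exactly the stated 80%.

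Much of this stands. It limits the size of the problem, and it means that only raw against transformed change is open for d. It does not close the gap. The SAP claims a multiplicity-adjusted threshold, which presupposes one test per contrast. It does not say that the choice will be blind to group, and GEE as usually run misses the level without any selection at all.

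A reader might go further in four ways that the documents do not support:

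- **That the investigators mean to choose on results.** Nothing says so; the plan simply does not exclude it.
- **That error is 5-6% or more per contrast.** Taking the smallest p-value of eight change, ANCOVA and rank tests gives about that in simulation, but it describes a worst-case search. It predicts nothing about this trial, and it is not a bound, since GEE and generalized linear models were outside the eight.
- **That the generalized linear model option inflates error.** The SAP names no family, link or variance estimator, so no error rate can be attached to it.
- **That the cited fold-changes are too small or large enough for d = 1.336.** That conversion needs an SD and a scale, and the documents give neither.

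**Conclusion.** The concern holds as a pre-specification gap with a measurable cost, and it should be fixed. The absence of one named test and scale is certain from the text. The sizes are conditional.

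- On lognormal data at the assumed correlations, with d in SDs of the log value, log ANCOVA has a power advantage of about 9 to 22 percentage points over log change or Group x Time.
- GEE with an uncorrected robust z-test gives 4.3% error in place of 2.5%. This needs only n = 12 per group and normal data on the analysis scale, but the SAP does not state which GEE variance or reference distribution it would use.
- A result-driven choice between two close options gives about 3.1-4.2%.

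The stated d = 1.336 is arithmetically correct and n = 12 per group is not in dispute here.

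**What to change.** Before any outcome is viewed by group, amend the SAP to:

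1. Name ANCOVA of log post-loading IL-1α/TP on log baseline IL-1α/TP as the single primary test for each within-platform contrast, at two-sided 0.025. It is within the SAP's own options and fits its expectation that spread rises with the mean. Another single baseline-adjusted test, or a fixed rule computed without group labels, would also secure the error rate.
2. State whether d = 1.336 refers to change on the raw or the log scale.
3. Label the other listed options, including Mann-Whitney on change, as sensitivity analyses that cannot replace the primary result.
4. Not use GEE with an uncorrected robust z-test as the primary analysis.

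The cost is SAP wording, one degree of freedom for the baseline, and the freedom to switch tests. There is a real downside if the data are closer to gamma. Log ANCOVA then gains nothing over raw change (22-68% against 23-66% power at the same fold-effects). At CV 1.5 with an assumed sevenfold group difference it is weaker than Mann-Whitney (38-47% against 48-60%). If the team expects such data, it should say so now and name the rank test instead.

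How one value per participant is formed, undetectable values, the body-fat stratum and measurements taken at withdrawal are separate details that this point does not settle.
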